	At 13-week visit, the following also will be done:				
	
 
Height, weight, blood pressure/pulse
 
				
	
 
Blood draw for central lab measurement of HbA1c, lipids, creatinine
 
				
	
 
PRO surveys completed, including frequency of non-severe hypoglycemia during the prior 3 months
 
				
	
 
At the completion of the RCT, participants will be transitioned back to their pre-study insulin regimen and have a safety contact after 3 ± 1 days.
 
Additional visits and contacts may occur at investigator discretion
 
				
	Exercise and Meal Challenges				
	• All participants in the AID group will perform the meal challenges and all participants in the AID group will perform the exercise challenges unless ineligible due to cardiac or other safety concerns.				
	• Each participant will perform 3 meal and 3 exercise challenges during the RCT. This will include a full bolus, half bolus, and no bolus meal, as well as three one-hour exercise periods (with at least 30 minutes moderate				

PARTICIPANT AREA	DESCRIPTION
	exercise). All challenges will be performed unsupervised at home, with required study team contacts before and after each challenge. For each exercise challenge, an individual (care partner) capable of providing treatment for severe hypoglycemia will need to be present.
	• Approximately 25% of each type of challenge (meal or exercise) will be performed on 3 consecutive days within each of the following 4 periods time from randomization: 1-2 weeks, 3-4 weeks, 5-6 weeks, 7-8 weeks. Challenges that cannot be scheduled during these time periods or challenges that need to be rescheduled may be performed, if necessary between weeks 9 and 13.
	• Participants will be instructed to communicate with study staff within one day prior to each challenge to review procedures and to have a contact with study staff after the completion of each challenge within one day.
	Study Safety Plan
	Participants will be given a blood glucose and ketone meter to use throughout the study and will be trained on their use by qualified staff. BGM readings will be performed in accordance with the study safety plan and per CGM manufacturer instructions. Ketone readings will be performed per the study safety plan, based largely on the development of symptoms suggestive of ketosis.
	Site investigators may adjust insulin delivery profile settings ONLY for safety concerns as needed throughout the study in accordance with their clinical practice. Reasons for the change will be documented in the CRF.
	A Data and Safety Monitoring Board will provide study oversight. All severe hypoglycemia, DKA, and HHS events will be reported expeditiously to the DSMB as described in section 9.5.
	Analysis Plan
	At the end of the RCT, it is planned that the database will be locked and

- 42 The following table provides an overview of the schedule of study visits, phone contacts, and key
- 43 procedures.

#### 44 Table 2: Schedule of Visits and Procedures

Visit Designation	Screening	End of Run-in	Randomization (Day 0)	3d	1w	4w	8w	13w
Visit Window		*	**	±1da	±2d a	±4d	±4d	±4d
Visit (V) or Contact (C)	V	V	V	C	С	v	V or C b	V
Informed Consent/Assent	X							
Eligibility Assessment	X							
Medical history/ focused physical c	X							
Review medications and doses	X	X	X	X	X	X	X	X
Blood pressure, pulse, height & weight d	X		Xe			X	Xb	X
HbAlc (POC or local lab)	Xf							
Pregnancy test (for participants capable of becoming pregnant)	X		Xe					
HbA1c (central lab)			X					X
Lipids, creatinine (central lab)			X					X
C-peptide, glucose, GAD antibodies (central lab)			Х					
Subjective Numeracy Scale	X							L
Questionnaires/Surveys (PRO Assessments) g	X							X
Initiation of Study CGM h	X							_
Assessment of CGM Use		Х						
Study system training; dispense study insulin			Xi	X				 
Upload device data from home or at clinic visit	X	X		X	X	X	X	X
AE Assessment		X	X	X	X	X	X	X
EKG and assessment of eligibility for exercise challenges j	x							
Exercise and Meal challenges k						See below		

- 47 \*Clinic visit after 21-28 days for participants required to complete CGM run-in.
- To proceed to randomization, participant must have used CGM for at least 80% of the time during the most recent 14 days. *If this requirement is not met, the run-in phase can be extended for an additional 14-21 days at investigator discretion.*
  - The most recent 14 days of CGM data will be used as the baseline for analyses

\*\* Randomization Visit should be on the same day as the End of Run-in visit, following which closed-loop participants have
up to 14 days to begin study pump use. Pump training can occur over more than 1 session if necessary.

- a Target and windows for 3-day visit, and 7-day visit are calculated from study pump initiation date for AID group.
- b At 8 weeks, clinic visit or contact depending on whether participant is able to upload device data at home and whether
   investigator believes clinic visit is needed.
- c A focused physical exam will be performed by the study investigator or designee (a physician, fellow, nurse practitioner or a
- physician assistant). This will include parts of the exam relevant to device use, such as skin changes from device or insulin
   use. At screening, it may include physical exam techniques related to assessment of cardiovascular disease if participation in
   the exercise and meal challenges is being considered.
- d Vital signs (including blood pressure and pulse) and height and weight measurements may be obtained by non-study support
   staff according to the clinic's usual processes.
- e Not performed if Randomization Visit is same day as Screening Visit. May be performed at other visits at the discretion of
   the investigator.
- fCan be skipped if result is available from within prior 30 days
- g See section 8.3 for list of questionnaires to be completed; includes frequency of non-severe hypoglycemia during the prior 3
   months
- h Study CGM training provided and CGM use initiated for all participants except those who are experienced current users of
   the study CGM with at least 85% of readings available from the prior 14 days
- Only for participants assigned to AID group; initial training typically will be completed and AID system use initiated on day
- of randomization but if investigator does not believe that participant is ready to start the study pump, initiation of the study
- pump can be deferred for further training but initiation of the AID system must occur within 7 days of randomization. Insulin
   aspart will be provided for participants who prefer to use the study insulin.
- 74 jEKG not required if performed within prior 12 months
- 75 k Exercise and meal challenges:
  - All participants in the AID group will perform the meal challenges and all without a safety contraindication will perform the exercise challenges.
- Each participant will perform 3 meal and 3 exercise challenges during the RCT. This will include a full bolus, half bolus, and no bolus meal, as well as three one-hour exercise periods (with at least 30 minutes moderate exercise).
   All challenges will be performed unsupervised at home, with required study team contacts before and after each challenge.
- Approximately 25% of each type of challenge (meal or exercise) will be performed on 3 consecutive days within
   each of the following 4 periods time from randomization: 1-2 weeks, 3-4 weeks, 5-6 weeks, 7-8 weeks. Challenges
   that cannot be scheduled during these time periods or challenges that need to be rescheduled may be performed, if
   necessary between weeks 9 and 13.
- 86 87

76

77

# 2. Comparison with the Protocol

The author of this document confirms that this SAP is consistent with version 5.0 of the Protocol, exceptthe following:

- New formal analyses were added to compare the night following meal or exercise challenges with the previous 14 nights without any previous day challenge.
- 94 95

96 97

101

103 104

92

93

# 3. Statistical Hypotheses

The primary endpoint for this study is HbA1c at 13-weeks adjusted for baseline HbA1c. The intervention will be considered effective if the AID group is superior to the Control group using a statistical significance of  $\alpha$ =0.05 and the analyses specified below in Section 7 (i.e., p < 0.05).

102 The null/alternative hypotheses for the primary endpoint are:

- *Null Hypothesis*: There is no difference in mean HbA1c at 13 weeks between AID and Control
- *Alternative Hypothesis*: Mean HbA1c at 13 weeks is different for AID and Control.

Similarly, the null and alternative hypotheses for all the secondary efficacy endpoints in the hierarchyare:

- *Null Hypothesis*: There is no difference in the endpoint at 13 weeks between AID and Control
- *Alternative Hypothesis*: Endpoint at 13 weeks is different for AID and Control.
- 109

107

108

#### 110 111

### 4. Sample Size

112

The sample size of 330 randomized participants was selected to provide sufficient exposure to the AID system for regulatory purposes. Given the 2:1 randomization, this equates with a maximum of 220 using the AID system for 13 weeks. Assuming a 10% drop out rate in each group, there will be 200 using the system for 13 weeks.

117

HbA1c data from N=30 participants in the 2IQ pilot study were used to estimate the SD for the power
calculation. The SD for baseline values was 1.0%. Under the null hypothesis - assuming a similar SD at
follow-up, correlation of 0.3 with baseline, and a two-sided test with type 1 error at 5%, a sample size of
N=300 completers will be able to detect an HbA1c difference as small as 0.38% with 90% power. There
will be 85% power to detect a difference of 0.35% and 80% power for a difference of 0.33%.

- 123
- 124 125

# 5. Outcome Measures

- 126127 5.1. Primary Efficacy Endpoint:
  - Superiority in HbA1c at 13 weeks.
- 128 129

130	
131	5.2. Secondary Efficacy Endpoints:
132	
133	
 
Continuous CGM-measured endpoints during 13 weeks of follow-up:
 

134	
 
Time in range 70-180 mg/dL
 

135	$\circ$ Time in range 70-140 mg/dL
136	
 
Mean glucose
 

137	$\circ$ Time >180 mg/dL
138	$\circ$ Time >250 mg/dL
139	
 
CGM-measured prolonged hyperglycemia events (defined in Section 5.3)
 

140	$\circ$ Time <70 mg/dL
141	$\circ$ Time <54 mg/dL
142	• Area over the curve $(70 \text{ mg/dL})$
143	
 
Low blood glucose index
 

144	• CGM-measured hypoglycemia events (defined in Section 5.3)
145	• Coefficient of variation
146	$\circ$ Time >300 mg/dL
147	• Area under the curve $(180 \text{ mg/dL})$
148	
 
High blood glucose index
 

149	
150	• Binary CGM-measure endpoints during 13 weeks of follow-up:
151	• Time in range 70-180 mg/dL $>$ 70%
152	• Time in range 70-180 mg/dL improvement from baseline to 13 weeks $\geq$ 5%
153	• Time in range 70-180 mg/dL improvement from baseline to 13 weeks $\geq 10\%$
154	$\circ  \text{Time} < 70 \text{ mg/dL} < 4\%$
155	$\circ Time < 54 mg/dL < 1\%$
156	• Time in range 70-180 mg/dL $>$ 70% and time $<$ 54 mg/dL $<$ 1%
157	
158	• Binary HbA1c endpoints at 13 weeks:
159	$\circ$ HbA1c <7.0% at 13 weeks
160	• HbA1c $< 7.0\%$ at 13 weeks in participants with baseline HbA1c $> 7.5\%$
161	$\circ$ HbA1c <7.5% at 13 weeks
162	• HbA1c improvement from baseline to 13 weeks $>0.5\%$
163	• HbA1c improvement from baseline to 13 weeks $>1.0\%$
164	• HbA1c relative improvement from baseline to 13 weeks >10%
165	• HbA1c improvement from baseline to 13 weeks $>1.0\%$ or HbA1c $<7.0\%$ at 13 weeks
166	
167	• Insulin delivered during 13 weeks of follow-up:
168	• Total daily insulin (units and units/kg)
169	
 
Total daily bolus (units and units/kg)
 

170	
 
Total daily basal (units and units/kg)
 

171	• Percentage of insulin units delivered as basal.
172	
173	• Weight at 13 weeks:
174	• Weight (kg)
175	
 
Body mass index
 

176						
177	Other Endpoints at 13 weeks:					
178	• Total cholesterol					
179	• HDL cholesterol					
180	• LDL cholesterol					
181	
 
Triglycerides
 
					
182	• Creatinine levels					
183	
 
Blood pressure
 
					
184						
185	• Patient-reported outcome (PRO) measures:					
186	
 
Administered at Screening only:
 
					
187	
 
Subjective Numeracy Survey – 8 items and 2 subscales (abilities and preferences)
 
					
188	and total score					
189	• Administered at Baseline and 13 weeks:					
190	
 
Type 2 Diabetes Distress Assessment System (T2-DDAS Combined - Core and
 
					
191	Source) $-29$ items, and with 1 major $+7$ minor subscales					
192	
 
DAWN Impact of Diabetes Profile (DIDP) - 7 items and total score
 
					
193	
 
Diabetes Impact and Satisfaction (DIDS) Scale – 11 items and two subscale
 
					
194	scores (device satisfaction and diabetes impact).					
195	
 
PROMIS Sleep-Related Impairment Questionnaire - 8 items and total score
 
					
196	
 
System Usability Scale (SUS) - 10 items and total score
 
					
197	
 
Hypoglycemia Fear Survey II – 33 items and two subscale scores (worry and
 
					
198	behavior)					
199	
 
NICE-approved Quality of Life (EQ5D-5L) - 5 items
 
					
200	
 
Study-specific survey that measure insulin management and dosing with meals –
 
					
201	2 items					
202	
 
Hypoglycemia Frequency Last 3 Months Survey – 4 items
 
					
203						
204	• Safety measures:					
205	
 
Severe hypoglycemia
 
					
206	
 
Diabetic ketoacidosis
 
					
207	
 
Hyperosmolar hyperglycemic syndrome
 
					
208	• Other serious adverse events					
209	
 
Unanticipated adverse device effects
 
					
210	• Hypoglycemia and prolonged hyperglycemia endpoints listed as effectiveness endpoints					
211	
 
Infusion set failures
 
					
212	
 
Other device malfunctions/device issues
 
					
213	• Cardiovascular events					
214						
215						
216	5.3 Calculation of Overall CGM Metrics:					
217	• Two Weeks of Baseline : The last 14 days of personal CGM data before enrollment or last 14					
218	days of CGM run-in data before randomization will serve as baseline. If a participant has <72hr					
219	of data in the last 14 days of CGM personal or run-in and if more CGM data are available					
220	beyond the 14 days, then will go backwards 24hr at one time until the minimum of 72hr of CGM					

data are reached. At least 72hr of data during baseline are required for the glycemic metrics to becalculated. These are Dexcom sensor data.

- Thirteen Weeks of Follow-up: All CGM data following the randomization will be included. 223 • Since the meal and exercise sessions are designed as challenges to the system and the data to be 224 analyzed for possibly induced safety events, the CGM data between the start of the meal or 225 exercise and 6:00AM next morning will be analyzed separately (see Sections 5.4 and 5.5 below) 226 and not included here. If the 13-week visit is more than 13 weeks after the randomization visit 227 for a participant, then the CGM data will be truncated at 13 weeks (i.e., 91 days). At least 168hr 228 229 of data during these 13 weeks of follow-up are required for the glycemic metrics to be calculated 230 and for a participant to be included in the glycemic analyses. These are either Tandem pump CGM data or Dexcom CGM data if obtained to fill any Tandem data gaps. 231
- All CGM metrics during baseline and follow-up periods will be calculated giving equal weight to
   each sensor reading for each participant.
- Calculation of CGM metrics for the treatment group comparisons will exclude the challenges and the period through 6AM on the day following the end of the challenge. CGM metrics during and following the challenges will be reported separately as described in Sections 5.4. and 5.5; while an overall analysis will be performed for all CGM data in the AID group (i.e., including the challenge data) as described in Section 17.
- CGM-measured prolonged hyperglycemia events are defined as ≥90 cumulative minutes with CGM glucose >300 mg/dL within a 120-minute period (the participant becomes eligible for another prolonged hyperglycemia event after the CGM glucose is <180 mg/dL for ≥15

   consecutive minutes).
- CGM-measured hypoglycemia events are defined as ≥15 consecutive minutes with CGM glucose <54 mg/dL (the participant becomes eligible for another hypoglycemia event after the CGM glucose is ≥70 mg/dL for ≥15 consecutive minutes). For each of these metrics, the number of events per week is calculated for each participant and each metric is then analyzed as a continuous variable as described below.

- 248 249

257

258

259

260

261

### 250 **5.4 Calculation of CGM Metrics for Meal Challenges**

- The meal challenges will happen and the metrics will be calculated only during the 13 weeks of
   follow-up in the AID group, and are based on either Tandem pump CGM data or Dexcom CGM
   data if obtained to fill any Tandem data gaps.
- Will be calculated only if the meal challenge session was recorded on the CRF. The date-time of
   the challenge-related events, along with other relevant details about the challenge will be
   recorded on the CRF and will be tabulated.
  - All data between the start of the meal challenge and 6:00AM next morning will be included.
  - For each meal, two different periods will be considered, and two separate glycemic metrics will be calculated:
  - During and two hours following the end of the meal the period between the start and 4 hours following the end of meal as recorded on CRF, and
- 262 > Overnight following the meal the period between 4 hours following the end of the meal and 6:00AM next morning.

- At least 2hr (or 24 CGM readings) are required for each one of the two periods associated with an individual meal session for the CGM metrics to be calculated.
  - Each CGM reading during a meal session will be given equal weight.
- The unit of analysis is an individual meal challenge session and any participant with at least one meal challenge completed will be included in these analyses.
  - The metrics calculated and reported here will include % time below 54, 70, 70-180, above 180, 250, 300 mg/dL and mean glucose.
- The above glycemic metrics will be calculated during the night following the meal challenge (10PM to 6AM) and will be compared with the corresponding metrics calculated during 14 nights without any challenge in the previous two days. Nights prior to the challenge will be used if available, then nights subsequent to the challenge if needed to obtain 14 total nights. The nights will be pooled together when compared with the night following the meal challenge. At least 6hr of CGM data are required for the night following the meal challenge and at least 72hr are required for the pooled 14 nights for these metrics to be calculated and formally compared.

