710 711 712 713		Only begin the meal challenge if CGM glucose is between 70 mg/dL and 200 mg/dL and CGM trend arrow is not rapidly rising (straight up arrow). Subjects with hyperglycemia > 200 mg/dL will reschedule their challenge for another time. If < 70 mg/dL, carbohydrate treatment can be given, after which the meal challenge can continue.
714 715 716		Consume at least 50 grams carbohydrate for the meal. Each participant will use the same meal for all of their meal challenges in the study. Participants will be encouraged to use the same frozen entrée of their choice for consistency.

- Write down the start and end time of eating the meal, as well as the meal content (to include amount of carbohydrate, protein and fat) on the study provided logbook.
- 5. Not give an additional bolus for up to 3 hours after the meal challenge, unless BG is above 300 mg/dL for more than 1 hour, or symptoms of hyperglycemia develop.
- 721 6. Not take additional carbohydrates for up to 3 hours after the meal challenge, unless BG is < 70 mg/dL, or symptoms of hypoglycemia develop.
 - 7. Not exercise for 3 hours after the meal challenge.
 - 8. Notify the site within 24 hours after completion of each meal challenge.
- 725 9. The meal challenge will end 3 hours after the meal is completed.
- If a meal challenge needs to be rescheduled due to out-of-range glucose value or an unforeseen circumstance, it should be completed on a separate day (same meal, lunch or dinner) as soon as
- 728 possible.

724

729

740

741

742

743

744

745

746

747

748

749750

751

752

753

754 755

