#### 456 **8.3 Meal and Exercise Challenges Analyses**

- There will be a descriptive and a formal comparison for the analyses during the meal and exercise
  challenge. First, the descriptive analyses for the selected glycemic mentioned in Sections 5.4 and 5.5 and
- 458 challenge. First, the descriptive analyses for the selected glycemic mentioned in Sections 5.4 and 5 459 insulin metrics mentioned in Section 5.2 will include summary statistics (mean  $\pm$  SD or median
- 40 (quartiles)), scatterplots, boxplots, and/or individual meals or exercise CGM and insulin tracings. Meals
- 461 will be grouped by the two periods (during plus up to 4hr after the end of meal and nighttime following
- the meal and until 6AM on the day following each challenge), type (lunch and dinner), amount of
- 463 carbohydrates, and announcement in the pump or not.
- Exercises analyses will be grouped by the two periods (during plus up to 2hr after the end of exercise
  and nighttime following the exercise and until 6AM on the day following each challenge); and
  additionally grouped by length, intensity, or type of exercise.
- Insulin metrics and any adverse events occurring during these challenges will be reported by type ofchallenge in addition to their being included in the overall safety analyses (Section 9).
- 469 The number of each challenge per participant will be tabulated.
- 470

- 471 For the formal analyses, the glycemic metrics during the nights following the meal challenge will be
- tabulated and compared with the corresponding metrics during 14 non-challenge nights calculated as
- 473 mentioned above in Section 5.4. A mixed linear model that adjusts for clinical center as random effect
- will be used for this purpose. A similar approach will be used for the exercise challenges.
- 475

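### SAP 5.4 labels a four-hour meal-challenge window as two hours, and its overnight period has no clock-time start, so after lunch or daytime exercise it begins well before night

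*SAP*

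**What the plan says.** **First meal window.** SAP 5.4 labels it "During and two hours following the end of the meal" and, in the same bullet, defines it as "the period between the start and 4 hours following the end of meal as recorded on CRF". SAP 8.3 describes it as "during plus up to 4hr after the end of meal".

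**Second meal window.** SAP 5.4 calls it overnight and defines it as "the period between 4 hours following the end of the meal and 6:00AM next morning". SAP 8.3 calls it nighttime. Each of the two periods needs at least 2 h of data (24 CGM readings).

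**Exercise.** SAP 5.5 has the same structure with a 2-hour cut, and there the label and the definition agree. The overnight period starts 2 hours after the end of exercise, and each period needs 1 h of data (12 readings).

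**A separate night.** The last bullets of SAP 5.4 and 5.5 also define a night of 10 PM to 6 AM. It needs at least 6 h of data and is formally compared with 14 pooled non-challenge nights.

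**Protocol.** Section 6.2 item 9 states: "The meal challenge will end 3 hours after the meal is completed". Item 5 tells participants: "Not give an additional bolus for up to 3 hours after the meal challenge", with stated exceptions. Items 6 and 7 put 3-hour limits on extra carbohydrate and on exercise, counted from the same point. The challenge meal may be lunch or dinner, and section 6.3 sets no time of day for exercise. Section 11.15.3 asks for CGM metrics from the challenge until 6 AM the next day and does not subdivide that span.

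**The concern.** A table built from SAP 5.4 could be headed with two hours and contain four. The four-hour window also goes beyond the challenge as the protocol defines it, and the SAP does not say why. Whether participants were still under the challenge restrictions in that extra hour depends on how items 5-7 and item 9 of Protocol 6.2 are read together.

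The second period is tied only to the end of the session. After a lunch or a morning exercise session it takes in the late afternoon or evening, a later dinner and the bolus for it, yet it is reported as overnight or nighttime.

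Challenge data are removed from the randomized CGM comparison, so these summaries are where results after no-bolus and half-bolus meals and after exercise are reported by period. If the labels do not match the hours, low glucose during the night is diluted by evening readings, and lunch and dinner sessions are not comparable under one heading.

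**Working it through.** **1. The SAP's data rule.** 24 readings / 2 h = 12 per hour (5.4) and 12 readings / 1 h = 12 per hour (5.5). Both give one reading every 5 minutes, so the rule is consistent.

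**2. First meal window.** The documents give no meal duration, so m = 15, 30 and 60 minutes are assumed. The length is m plus 2, 3 or 4 h. The share of the 4-hour window that falls after the protocol's challenge end is 1/(m + 4).

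| Meal | Label (+2 h) | Protocol end (+3 h) | SAP definition (+4 h) | Share after challenge end |
|---|---|---|---|---|
| 15 min | 2.25 h | 3.25 h | 4.25 h | 1/4.25 = 23.5% |
| 30 min | 2.5 h | 3.5 h | 4.5 h | 1/4.5 = 22.2% |
| 60 min | 3 h | 4 h | 5 h | 1/5 = 20.0% |

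**3. Status of the fourth hour.** If the 3 hours in items 5-7 are counted from the end of the meal, the limits lapse at hour 3 and the fourth hour is unrestricted. If they are counted literally from the end of the challenge, which item 9 places 3 hours after the meal, they run to 3 + 3 = 6 hours and the fourth hour is restricted. The text supports either reading.

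**4. Start of the overnight period.** Clock times are not in the documents and are assumed. For a meal ending at hour E (24-hour clock), the start is E + 4, the length is 30 - (E + 4), and the time before 10 PM is max(0, 22 - (E + 4)).

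| Meal ends | Period starts | Length | Before 10 PM |
|---|---|---|---|
| Lunch, 12:00 | 16:00 | 14 h | 6 h (43%) |
| Lunch, 13:00 | 17:00 | 13 h | 5 h (38%) |
| Lunch, 14:00 | 18:00 | 12 h | 4 h (33%) |
| Dinner, 18:00 | 22:00 | 8 h | 0 |
| Dinner, 20:00 | 00:00 | 6 h | 0 |

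For exercise the start is 2 hours after the session ends. A session ending at 10:00 gives 12:00 to 06:00, which is 18 h, of which 10 h (56%) fall before 10 PM.

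**5. Data minimum.** For a lunch ending at 13:00, readings from 17:00 to 19:00 alone give 2 x 12 = 24 and satisfy the rule. For exercise ending at 10:00, readings from 12:00 to 13:00 give 12 and satisfy it. In both cases an overnight result is produced with no reading after 10 PM.

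**The case against.** The strongest reply is that the label is a slip. Four hours appears in the definition, in the start of the next window and in SAP 8.3; two hours appears once, in wording that 5.5 shares and where it is correct. A programmer would most likely use four. That is probably right, and it is a reason to correct the label.

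A reader might infer four stronger things, and the documents do not support them:

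- **Three conflicting lengths for one measure.** Protocol 6.2 item 9 sets the length of the procedure, not of a CGM metric, and 11.15.3 sets no 3-hour cut. SAP 5.3 says the challenge data are examined for safety events the sessions may induce, and following glucose past the end suits that aim. Three versus four hours is an unexplained mismatch and a matter of choice. (SAP section 2 declares one departure from the protocol, a different one, but it refers to version 5.0 and the protocol at hand is 8.0.)
- **The fourth hour is free living and flatters the system.** Step 3 shows that this depends on the reading. The direction is not shown either: a correction bolus would lower glucose, eating would raise it. A 3-hour window would not exclude user boluses, because item 5 already allows them in stated circumstances.
- **Late hypoglycaemia after a challenge cannot be seen.** The formal 10 PM to 6 AM comparison includes time below 54 and 70 mg/dL. The descriptive figure dilutes night-time lows; it does not hide them from the whole analysis.
- **The treatment comparison is affected.** It excludes everything from challenge start to 6 AM, however that span is split.

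It is also fair that SAP 8.3 groups meals by lunch and dinner and lists individual tracings among its displays, so lunch sessions can be separated. The lunch period would still be mislabelled.

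**Conclusion.** The point holds as a labelling and definition fault in the descriptive challenge summaries of the AID group. The two-hour label contradicts its own definition; this needs no assumption. The 4-hour window extends one hour past the protocol's challenge end without explanation (20-24% of the window for meals of 15-60 minutes, durations assumed), and items 5-7 and 9 of Protocol 6.2 must be reconciled on what applies in that hour.

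The overnight period is not a night period after lunch or daytime exercise. For lunches assumed to end between noon and 2 PM, 43-33% of it precedes 10 PM; for dinners ending between 6 and 8 PM, none does. The data minimum does not ensure any night data. HbA1c, the hierarchical endpoints and the formal night comparison are unaffected. The point is worth acting on because the repair is cheap and these summaries report how the system performed under challenge.

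**What to change.** 1. In SAP 5.4, correct the two-hour label to match the window used. Either end that window 3 hours after the meal, in line with the challenge end in Protocol 6.2 item 9, or keep 4 hours, state the reason, and identify the fourth hour as after the challenge end. Use the same choice in 8.3.
2. Reconcile items 5-7 with item 9 in Protocol 6.2, so that the status of the fourth hour is known when the results are read. Which rule applies is for the protocol team.
3. In SAP 5.4, 5.5 and 8.3, start the overnight or nighttime period at the later of 10 PM and the end of the first window, and end it at 6 AM. The later-of rule is needed because a first window ending 3 hours after the meal passes 10 PM when dinner ends after 7 PM, and the 2-hour exercise window does so when exercise ends after 8 PM. A bare 10 PM start would make the two periods overlap.
4. Apply the minimum-data rule to that period, and report any hours between the first window and 10 PM as a separate rest-of-day period.

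The cost is SAP wording and a cut-off in the program, with no new data. The summaries gain one descriptive period and the overnight windows become shorter: 13 h becomes 8 h for a lunch ending at 1 PM, with 5 h moved to rest of day. When the first window ends by 10 PM, the new overnight period covers the same hours as the night already used in the formal comparison, so there is some duplication.
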